# Secondary outcomes

- 1. Units of blood products used (packed red blood cells, fresh frozen plasma, platelets, prothrombin complex concentrate, recombinant factor VIIa, cryoprecipitate) in the first 24 hours
- 2. Blood lactate concentration at patient arrival to hospital
- **3.** Coagulation profile (international normalised ratio, activated partial thromboplastin time, fibrinogen, platelet count) at:
  - a. hospital arrival;
  - b. end of treatment with study drug (i.e., immediately after administering the second dose of the study drug by 8-hour infusion);
  - c. 24 hours after the first dose of study drug.
- **4.** Vascular occlusive events (deep venous thrombosis, pulmonary embolism, myocardial infarction, stroke) up until 28 days or hospital discharge (whichever occurs first).
- 5. Ventilator-free days in first 28 days.
- 6. Mortality at:
  - a. 24 hours;
  - b. 28 days;
  - c. 6 months.
- 7. Proportion of deaths due to:
  - a. bleeding;
  - b. vascular occlusion (pulmonary embolus, stroke or acute myocardial infarction);
  - c. multiorgan failure;
  - d. brain/neurological injury.
- **8.** Cumulative incidence of sepsis up until 28 days or hospital discharge (whichever occurs first).
- **9.** Quality of life (World Health Organisation Disability Assessment Schedule (WHODAS) 2.0 and EuroQol 5-Dimension (EQ-5D)) at 6 months.

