## Randomisation

Trial packs are prepared by an independent pharmaceutical packaging company with either TXA or placebo. Packs are consecutively numbered, opaque, foil parcels with a tamper proof seal. Upon confirmation of eligibility, patients are randomised (1:1) to TXA or placebo, with the randomisation stratified by state and country participating in the study, and additionally by the presence of severe traumatic brain injury (TBI) defined by a Glasgow Coma Scale (GCS) <9 assessed at the time of randomisation.

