# Sample size

Targeting 90% power to detect an increase in a favourable GOSE outcome (scored 5–8) from 60% to 69% with TXA, this trial would require 592 patients in each arm (1184 total) with a twosided 5% significance level. In a protocol amendment (PATCH Protocol ANZIC-RC/ V.1.6 3 February 2020) accommodation for a 10% loss to follow-up, the required sample size was increased to 658 patients in each arm (1316 total).

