# Secondary and tertiary endpoint analyses

The binary secondary outcomes of vascular occlusive events (#4), mortality at 24 hours, 28 days and 6 months (#6) and incidence of sepsis to 28 days (#8) will be analysed using the same log-binomial regression modelling approach as the primary outcome. Cumulative mortality to 6 months will also be displayed with Kaplan-Meier curves. Blood product usage (#1) will be dichotomised as any/none and also analysed with log-binomial regression. The quantity of blood product usage among patients receiving the product will be summarised with medians and interquartile ranges, and compared between treatment groups using quantile (median) regression, reporting the difference in medians between treatment arms together with 95% Cls and p values. Analyses of blood lactate concentration (#2) (regardless of assay method) and coagulation profile variables at each time point (#3) will similarly use quantile regression to compare medians between treatment groups. Blood lactate concentration (#2) obtained by venous and arterial samples will each also be dichotomised at >3mmol, and a composite measure of >3mmol for either sampling method will be calculated. INR (#3) will be dichotomised at >1.3 IU, and fibrinogen (#3) at <1 g/L and at <2 g/L. These dichotomised variables will be analysed as binary variables as above. Ventilator-free days in the first 28 days (#5) will assign a value of 0 to patients dying within 28 days regardless of location at time of death, and a value of 28 days if never ventilated in ICU or never admitted to ICU. This will be analysed using quantile regression to estimate the difference in median ventilation-free days. The 4 causes of death (#7a,b,c,d) in patients that died at any time up to 6 months will be tabulated and reported descriptively. The cumulative incidence of each cause of death to 6 months will be displayed graphically taking into account the other competing causes of death, and with cause-specific hazard ratios estimated using Cox regression with censoring at the time of all other causes of death. A composite cause of 'potentially preventable death' will be calculated as any of bleeding, vascular occlusion and multi-organ failure. Comparison of median quality of life outcomes at 6 months (#9) between treatment arms will be analysed using quantile regression, with patients not alive at 6 months treated as having missing values (and see below), and with EQ-5D calculated using Australian weights (3).

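### Ventilator-free days: the difference in medians, the only planned comparison, can miss a moderate fall in mortality and is uninformative if about half or more of patients score 28

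*SAP*

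**What the plan says.** Outcome 5 in the SAP's list of secondary outcomes is "Ventilator-free days in first 28 days". Under Secondary and tertiary endpoint analyses, the scoring "will assign a value of 0 to patients dying within 28 days regardless of location at time of death, and a value of 28 days" to those who had no ventilation in ICU or were not admitted there. The comparison then follows: "This will be analysed using quantile regression to estimate the difference in median ventilation-free days".

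No rank-based, ordinal, mean or two-part analysis of this outcome is given. The second paragraph of the same section adds analyses that deal with death, but only for vascular occlusive events, sepsis and quality of life. Mortality at 24 hours, 28 days and 6 months is analysed separately as outcome 6, by risk ratio. The SAP states no expected mortality, share of patients ventilated, or distribution of ventilator-free days.

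**The concern.** The scoring creates a scale with a block of patients at each end: deaths at 0 and the never-ventilated at 28. The median depends only on where the middle patient falls. A prevented death therefore counts only by shifting which patient is in the middle, whether the survivor ends at 5 days or at 28. Once the block at 28 holds more than half of an arm, the middle patient is inside it and the median cannot move.

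The outcome has its own test and will be reported as a difference in days. A result of 0 days could be read as no effect on survival or ventilation when the summary could not have shown one. This does not come from rounding. It persists when ventilation time is continuous.

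**Working it through.** **Inputs from the SAP.** Sample size gives "Targeting 90% power to detect an increase" in favourable GOSE "from 60% to 69% with TXA", with "592 patients in each arm (1184 total) with a twosided 5% significance level". Under Randomisation, "patients are randomised (1:1) to TXA or placebo". Scoring and method are as quoted above.

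**Reproducing the plan's own figure.** With p1 = 0.60, p2 = 0.69 and mean 0.645:

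n = [1.960·√(2·0.645·0.355) + 1.282·√(0.60·0.40 + 0.69·0.31)]² / 0.09² = 592 per arm.

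Allowing for 10% loss, 592/0.90 = 657.8, so 658, as stated: "the required sample size was increased to 658 patients in each arm (1316 total". The sample size is sound. The SAP gives no figure for ventilator-free days, so everything below uses assumed inputs and 592 per arm.

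**Ceiling.** Let d be the proportion dead by day 28 and v the share of survivors never ventilated. The share of an arm at 28 is (1 − d)·v. Assume d = 20% versus 14% and v = 65%:
- Placebo: 0.80 × 0.65 = 0.52. TXA: 0.86 × 0.65 = 0.559. Both exceed one half, so both true medians are 28 and the true difference is 0 despite a 6-point fall in deaths.
- The standard error of the placebo share is √(0.52 × 0.48/592) = 0.0205, and (0.52 − 0.50)/0.0205 = 0.97. The placebo median is therefore 28 in about 83% of trials, and the TXA median in over 99%. The observed difference is exactly 0 in roughly 83% of trials.

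**Below the ceiling.** With identical survivors, the overall median is the (0.5 − d)/(1 − d) quantile of survivors' scores:
- d = 20%: 0.30/0.80 = 0.375. d = 14%: 0.36/0.86 = 0.419. The median moves from the 37.5th to the 41.9th percentile of survivors.
- Example: v = 35%, ventilation days log-normal (mu 1.8, sigma 0.9). Among ventilated survivors these percentiles are 0.375/0.65 = 0.577 and 0.419/0.65 = 0.644. The medians are 28 − exp(1.8 − 0.9 × 0.194) = 22.9 and 28 − exp(1.8 − 0.9 × 0.369) = 23.7, a shift of 0.7 days.
- At d = 40% versus 30% the quantile moves further, from 0.10/0.60 = 0.167 to 0.20/0.70 = 0.286, so the median responds much more.

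**Simulated power.** The model takes a score of 0 if dead, 28 if never ventilated, and otherwise 28 minus log-normal ventilation days (mu 1.8 or 2.2, sigma 0.9), floored at 0. The median difference was tested with a bootstrap standard error and compared with Mann-Whitney. With 300 to 400 trials per scenario, the simulation standard error is at most about √(0.25/300) = 2.9 points.

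| Assumed effect | Survivors never ventilated | Median | Rank |
|---|---|---|---|
| Deaths 20% vs 14% only | 10–50% | 16–24% | 31–44% |
| Deaths 20% vs 14% only | 65% | 1–3% | 46–53% |
| Deaths 20% vs 14%, ventilation about 18% shorter | 10–35% | 75–95% | 79–98% |
| Ventilation about 22% shorter, deaths 20% in both arms | 20–50% | 23–67% | 13–56% |
| Deaths 35% vs 27% only, long ventilation | 10–20% | 41–47% | 52–58% |

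Under no effect, rejection was about 3–7% for the rank test and 1–7% for the median, so the rank test's gain is not bought with false positives.

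**A second model.** This used scores in whole days, a bootstrap percentile interval, and never-ventilated shares taken over all placebo patients:
- Deaths 22% to 15%, 30% never ventilated, median ventilation 5 days: both true medians are 24, although the mean rises 1.4–1.6 days. Power is 3–7% for the median and 29–52% for ranks.
- Deaths 22% to 15%, 55% never ventilated: the observed difference is exactly 0 in 98–99% of trials. Power is 0% and 16–63%.
- Deaths 40% to 30%, median ventilation 10–14 days, 10–20% never ventilated: the median moves 7–9 days. Power is 49–73% and 50–80%.

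**The case against.** The strongest reply is that the better test depends on the kind of effect. If TXA shortened ventilation and left deaths unchanged, the median would have more power than ranks at 20–50% never ventilated. Ventilation time is also the part of this outcome that the mortality analyses do not cover. This stands, and it rules out replacing the median regression.

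A reader might infer that the median hardly responds to prevented deaths in any setting. The documents do not support that. With high mortality and long ventilation it moves several days and comes close to the rank test. Deaths of 40% by day 28 would, however, use up the whole 40% unfavourable share assumed for placebo at six months, so that case is at the edge of the design.

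A reader might also infer that this trial will hit the ceiling. The SAP cannot show that. Entry requires a coagulopathy score of at least 3, and GCS below 9 is a stratification factor, so many patients may be ventilated. Against this, neither ventilation nor ICU admission is an entry criterion, and the scoring rule itself provides for patients never admitted to ICU. The ceiling is possible but not established.

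Deaths are also analysed directly, and the 28-day mortality risk ratio will appear in the same principal manuscript. That limits the harm but does not make a 0-day difference informative about ventilation. Nor does the SAP say that this outcome is meant as a test of mortality; scoring deaths as 0 may only keep them in the analysis.

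Finally, ranks ignore distances too. True, but they use every patient's position rather than the middle one alone, which is why they still register prevented deaths at the ceiling.

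**Conclusion.** The point holds in a limited form. The ceiling follows from the SAP's own scoring and needs no assumption about the treatment effect: with more than half of each arm at 28, the median difference is 0. Whether this will happen, and how much power is lost below it, rests on mortality, ventilation shares and durations that the SAP does not give.

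For a deaths-only fall from 20% to 14%, the assumed models put the median at roughly half the power of a rank test below the ceiling and close to no power at it. The ordering reverses for a pure effect on ventilation time. Because the study hypothesis names reduced mortality, the first case cannot be set aside.

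This is a weakness in one secondary outcome, worth correcting because the remedy is nearly free. Nothing is misstated or contradictory, and the primary analysis, the sample size and the mortality analyses are unaffected.

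**What to change.** Under Secondary and tertiary endpoint analyses:

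- Keep the 0 and 28 scoring and the median regression.
- Prespecify alongside it a rank-based comparison of the same values, as a Mann-Whitney probability or win odds with 95% CI and death as the worst rank.
- State that this becomes the main comparison of ventilator-free days if either arm's median is at or near 28. Define near in days before unblinding, so that the choice is not made on the results.
- Report ventilator days in survivors next to the 28-day mortality risk ratio already planned, so that both components are visible. The survivor summary is descriptive, since survivors are selected after randomisation.

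The cost is some SAP wording and one extra analysis of data already collected, with no change to sample size. The downside is an effect expressed as a probability or odds rather than in days, which the retained median difference offsets.

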# **Analysis Populations**

## A. Intention-To-Treat (ITT) population

The ITT population will consist of all randomised patients.

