# Primary outcome analysis – favourable 6-month GOSE score

#### ITT analysis

The binary primary outcome of favourable GOSE (scores 5-8) will be compared between treatment groups using a risk ratio together with a 95% confidence interval and p-value, estimated by a log-binomial regression model. If model convergence is not achieved, then Poisson regression with robust standard errors will be applied. Supplementary analyses will adjust for the randomisation stratification variables of country/state and GCS<9 as fixed effects in the regression model. These analyses will use the 6 month GOSE regardless of the actual duration at the time of measurement. The number of patients with 6 months GOSE assessed prior to 4 months or beyond 8 months will be tabulated, and sensitivity analyses excluding these patients will be performed.

If the proportion of patients missing the primary 6 month GOSE outcome exceeds 5%, a supplementary analysis using multiple imputation of the missing outcomes using chained equations will be employed using relevant baseline and postbaseline variables in the imputation models that are predictive of GOSE, or of GOSE being missing, and constructed separately for each treatment arm. Patients who withdrew consent for any data to be used will not be included in these imputations. This multiple imputation analysis will be regarded as supplementary.

Post hoc sensitivity analyses will make adjustment for any variables exhibiting substantial imbalance across treatment arms at baseline.

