
Additional analyses of each of the vascular occlusive events (#4) and sepsis (#8) at 28 days will be performed to take into account the competing risk of death. This will use cumulative incidence functions with estimated incidence at 28 days, with the incidence compared across treatment groups using risk ratios with 95% CIs derived using the delta method. For analysis of quality of life outcomes at 6 months, for patients not alive at that time a value of 0 will be imputed for the EuroQol 5-Dimension (EQ5D) summary and VAS scores (3). For the WHODAS scale, in the absence of published guidelines for addressing mortality, a score of 61 will be imputed, placing death as worse than the maximum scale score of 60. These modified quality of life outcomes will also be analysed using quantile regression. Supplementary analyses of these outcomes will use inverse probability of death weighting rather than imputation of values to accommodate truncation by death.

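### The death-value quality-of-life analysis scores every known death but states no handling for survivors with missing scores, so its between-arm difference can be biased

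*SAP*

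**What the plan says.** The SAP section Secondary and tertiary endpoint analyses gives three analyses of outcome #9.

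- Survivors only, with deaths set to missing: "Comparison of median quality of life outcomes at 6 months (#9) between treatment arms will be analysed using quantile regression".
- Death values: "For analysis of quality of life outcomes at 6 months, for patients not alive at that time a value of 0 will be imputed", which applies to the EQ-5D summary and VAS. For WHODAS, "a score of 61 will be imputed, placing death as worse than the maximum scale score of 60". Then: "These modified quality of life outcomes will also be analysed using quantile regression".
- Weighting: "Supplementary analyses of these outcomes will use inverse probability of death weighting rather than imputation of values to accommodate truncation by death".

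Each deals with death. None deals with a living patient who has no WHODAS, EQ-5D summary or VAS score.

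The SAP does plan for missing data elsewhere. Under the ITT analysis of the primary outcome, if more than 5% of 6-month GOSE values are missing, "a supplementary analysis using multiple imputation of the missing outcomes using chained equations will be employed". It is built separately by arm, labelled supplementary, and confined to GOSE.

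General principles assigns secondary outcomes to the ITT population, and Analysis Populations defines it: "The ITT population will consist of all randomised patients".

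**The concern.** The death-value analysis is the version of outcome #9 that comes closest to covering everyone randomised. It gives every known death a number and leaves living non-responders without one. Quantile regression drops records with no outcome, so the analysed set becomes all known deaths plus the survivors who answered. That is not the ITT population, and its mix of dead and living depends on the response rate as well as on treatment.

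The two existing devices do not repair this. The GOSE imputation supplies no WHODAS or EQ-5D score, and the weighting is stated to address truncation by death, not non-response among the living.

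At stake is the comparison of graded recovery between arms. If mortality, survivors' disability or response differs by arm, part of the reported difference in medians reflects who answered. With no method fixed now, one would have to be chosen when the separate quality-of-life manuscript is written, with the data in view.

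**Working it through.** **1. The plan's own figures.** The SAP gives no figure for outcome #9; its only loss figure is in Sample size. For 60% versus 69%, 90% power and two-sided 5% (pooled variance, no continuity correction), n = 592 per arm, and 592 / (1 − 0.10) = 658. Both agree with the SAP.

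**2. Share of deaths in the analysed set.** Let m be 6-month mortality and s the fraction of survivors without a score (both assumed).

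Share = m / [m + (1 − m)(1 − s)]

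- m = 20%: 21.7% at s = 10%, 23.8% at s = 20%, 26.3% at s = 30%.
- If 10% of all randomised patients are lost and all are survivors: 0.20 / 0.90 = 22.2%. For m = 30%: 0.30 / 0.90 = 33.3%.

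**3. Effect on the WHODAS median difference.** Assumed placebo mix: 20% dead, 20% GOSE 2–4, 60% GOSE 5–8. Assumed scores: normal, mean 42 (SD 9) in GOSE 2–4 and mean 22 (SD 8) in GOSE 5–8. Deaths are at 61. With response r₁ in GOSE 2–4 and r₂ in GOSE 5–8, the analysed median x solves

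[p₁r₁Φ((x − 42)/9) + p₂r₂Φ((x − 22)/8)] / (d + p₁r₁ + p₂r₂) = 0.5

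where d, p₁ and p₂ are the proportions dead, in GOSE 2–4 and in GOSE 5–8. Differences are TXA minus placebo; negative favours TXA.

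*Scenario A:* TXA moves 9 points from GOSE 2–4 to 5–8 (the SAP's 60% to 69%), mortality equal. Full response: 26.61 − 28.98 = −2.4.

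| Response (GOSE 2–4 / 5–8) | Loss, placebo | Estimated difference | Bias |
|---|---|---|---|
| 87.5% / 87.5% | 10% | −2.5 | −0.1 |
| 75% / 91.7% | 10% | −2.1 | +0.3 |
| 50% / 85% | 19% | −1.7 | +0.7 |
| 40% / 90% | 18% | −1.4 | +1.0 |
| 90% / 75% | 17% | −3.1 | −0.8 |

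Bias is computed before rounding. Placebo loss = 0.20(1 − r₁) + 0.60(1 − r₂); for example 0.20 × 0.50 + 0.60 × 0.15 = 0.19.

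*Scenario B:* TXA moves 4 points from death to GOSE 5–8. True difference −1.24. With 75% response in all survivors the estimate is −1.72, so purely random non-response biases the result once mortality differs. With 50% / 85% response it is −1.31: lost disabled survivors and over-weighted deaths pull the median in opposite directions and nearly cancel.

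*No effect, same response in both arms:* the difference is 0 for every response pair above; only the arm medians move.

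**4. A second score model.** Survivor WHODAS = 12 + 48 × Beta(1, 2), 2,000,000 simulated patients per arm.

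- Mortality 22% versus 17%, 10% of survivors missing at random: −1.5 becomes −1.7. With 25% missing: −1.5 becomes −2.1.
- No effect, mortality 22% in both arms, 20% of placebo and 10% of TXA survivors missing: 0.0 becomes −0.8.
- Mortality 22% versus 17%, TXA survivors more disabled (Beta(1.15, 2)), 25% missing: +0.4 becomes −0.2, a change of sign.

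**5. Does a repair work?** Mortality 22% versus 17%, with response of 90% in less severe and 60% in more severe survivors: true −1.49; responders only −1.96; responders weighted by the inverse of their response probability −1.48. Missingness was made to depend on the modelled severity alone, so this shows only that the method works when its assumption holds.

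**The case against.** The strongest reply is that the bias is small and conditional. The SAP gives no completion rate for WHODAS or EQ-5D, overall or by severity. At the plan's own 10% loss, Scenario A is off by 0.1 to 0.3 points on a scale with a maximum of 60. Under the same assumptions the sampling standard error of that difference, with 592 per arm, is about 1.1 points. The larger figures need roughly twice the planned loss. Outcome #9 is secondary, already has three analyses, and is reported apart from the principal manuscript. All of this stands and limits the weight of the point.

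A reader might infer more than the SAP supports:

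- *That severely disabled survivors will be under-represented.* Nothing in the SAP says that they respond less often. It is plausible, but an assumption.
- *That the treatment effect will be shrunk, or exaggerated.* The direction depends on who responds: −2.4 becomes −1.7 or −3.1.
- *That dropping non-responders is a stated rule.* It is the default result of a plan that is silent.
- *That a shift from death to severe disability would falsely look like a gain.* Death is deliberately scored worst, so in this analysis such a shift is a gain by construction.
- *That imputation should become the main analysis of outcome #9.* The SAP keeps imputation supplementary even for GOSE, so the reverse for a secondary outcome would invert its own order.

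What the reply does not remove is the gap. Handling missing outcomes is a matter for the analysis plan; this SAP does it for GOSE and for deaths, and omits living non-responders.

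**Conclusion.** The concern holds in a limited form. The SAP fixes values for all known deaths and no handling for survivors with missing quality-of-life scores, so the death-value analysis over-weights deaths unless every survivor responds. That much is arithmetic.

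Bias in the between-arm difference is conditional: it can arise, in either direction, when mortality, survivor disability or response differs between arms. Under the assumed mortality, score distributions and response rates, it is about 0.1 to 0.3 WHODAS points at 10% loss and up to about 1 point at roughly 20% loss. With no treatment effect and equal response there is none. EQ-5D was not modelled; the same gap applies to it, but no size is claimed. The point is minor to moderate and leaves the primary outcome untouched.

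**What to change.** In Secondary and tertiary endpoint analyses, add a supplementary analysis of outcome #9 in line with the GOSE imputation and its 5% trigger:

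- For patients alive at 6 months with a missing WHODAS, EQ-5D summary or VAS, multiply impute the score by chained equations separately by arm. Use 6-month GOSE (observed or imputed), age, GCS<9, country/state and other collected predictors. Alternatively, weight responding survivors by the inverse of their probability of response.
- Assign the death values (0 or 61) afterwards, then run the planned quantile regression.
- Exclude patients who withdrew consent for use of their data, as the GOSE imputation already does.
- Tabulate quality-of-life completion by arm and GOSE category.
- Add a missing-not-at-random sensitivity analysis. This matters most if GOSE is often missing together with the quality-of-life scores, because the main predictor would then itself be imputed.

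The planned analyses stay in place. The cost is one SAP paragraph and some extra analysis work, with no new data collection. The result will rely on missingness being explained by the variables used.
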